- 5) Visually displaying any piece of mail listing the subject's name and address
- 6) Asking the subject to verbally state their name

Baseline Surveys:

The Locator Form and Baseline Assessment is completed at the time of enrollment. These are completed electronically and may be done in person using a study laptop or remotely via telephone or video call.

Randomization. Study participants will be randomized to receive the Education or Motivational intervention at a 1:1 ratio. Randomization will be performed at the participant level, meaning that in general, participants within a site will be assigned to different groups. Randomization will be stratified by site as well as by key participant characteristics such as prior infection/vaccination, to ensure balance. Random assignments will be provided via a web-based API, with the touchpads programmed to retrieve an assignment at the appropriate time and deliver message to staff so they can direct the participant to the appropriate room.

C3 Intervention: COVID-19 Testing and Vaccination Network Intervention Condition. Study participants randomized to the Motivational Intervention will receive the intervention using a social network diffusion approach. The Motivational intervention will be based upon a previous workshop divided into four learning and practice modules (Table 2 below).

Table 2. Motivation Intervention**C3 Intervention Components adapted from RADx-UP Phase I and PrEPChicago.**

Strategy	Content	Duration	Intervention Strategy Source(s)
Fact or Myth session with sub-group role-play	COVID-19 prevention Fact or Myth session 1) different types of tests and vaccines; 2) technology, clinical development and effectiveness; 3) vaccine dosing administration and relationship to prior COVID-19 infection; 4) potential side-effects; and 5) how to access it.	45 minutes	PrEPChicago/RADx-UP Phase I
Situation Appropriate COVID-19 Prevention	Knowing the network member's COVID-19 history (ie. prior infection, recent exposure). Discussion of indications for testing (ie. COVID-19 symptoms, known exposure) and vaccination post-infection. Testimonials around misinformation, correction and discussion.	45 minutes	RADx-UP Phase I

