Empowering Appropriate COVID-19 Prevention	Reasons for vaccination and group-selected topics of discussion (1) prompting individuals to generate and verbalize their own reasons for testing and vaccination and (2) allowing individuals to choose testing and vaccination topics most relevant	30 minutes	Project Voice/RADx-UP Phase I
Network engagement and Motivational Interviewing	Effective Delivery of Information and MI strategy discussion (1) how the conversation will be raised, (2) how potential barriers to testing and vaccination will be addressed, (3) how network members can be assisted to make a visit to a COVID-19 services site, and (4) what sort of follow-up is required to motivate network members who have yet to be tested/vaccinated after earlier conversations.	60 minutes	PrEPChicago/RADx-UP Phase I

The first module introduces COVID-19 prevention (testing and vaccination) in an interactive *Fact or Myth* activity that will provide an overview for understanding the implications of COVID-19 tailored to the specific audience.

The second module builds upon RADx-UP Phase I to provide situation-appropriate recommendations given the diversity of COVID-19 spaces network members find themselves in (previously infected, congregate setting, recently exposed etc.). This module also utilizes video testimonials developed in RADx-UP Phase I that feature community members with lived testing and vaccination experiences. The videos will be viewed in a group setting using a large computer or TV monitor. A list of videos will be provided with descriptive information about the factual content they present. Content will be updated in real time as testing/vaccination recommendations change, and these changes will also be matched to outcome assessment.

The third module will ensure participants actively engage with COVID-19 prevention information and content. We will facilitate an empowerment process that will direct participants to choose testing and/or vaccination topics that they would like to consider (e.g., prevent health risks, protect others from infection, vaccine safety, future regret) and then prompt them to generate and verbalize their own reasons for testing/vaccination based on those topics.

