Each mini-booster consists of four components: 1) collecting information about specific network members that the participant has engaged with about testing/vaccination (both Education/Motivational arm); 2) devising personalized conversational strategies for approaching these network members (C3); 3) troubleshooting communication barriers (C3); and 4) setting personal outreach goals (C3). The Education condition will also have a 30-day follow-up conversation and review of any questions that may come up. Measurement of testing/vaccine barriers for participants and participants' report on network members will be collected during the booster session for both Motivational and Education conditions. The same staff member who provided the initial intervention will conduct the booster with a given participant in order to continue rapport building.

Subject Compensation. Compensation will be provided for study participation- up to \$200 will be provided for study participation and all participants will receive snacks/refreshments during the Education and Motivational arm sessions. Compensation will be provided as follows:

- 1) \$150 will be provided for completing the first study interaction (i.e., consent, ROI, Education or Motivation group session, baseline survey and short locator form);
- 2) \$25 for completing the second study interaction (i.e., short phone booster session and second survey 30 days later); and
- 3) \$25 for completing the third study interaction (i.e., final survey 90 days post enrollment).

Payments will be in cash, gift cards or e-payments such as CashApp, PayPal or Venmo.

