Primary Outcomes. Two primary outcomes will be assessed at the level of the participant: the probability of receiving at least one 1) test and 2) vaccination dose within 3 months of baseline. Outcomes will be ascertained specifically by testing/vaccine registry data held by city and state held vaccine registries (Letters, [name], [name], [name]). Study participants will sign release of information forms, as in RADx-UP Phase I, in order for study staff to obtain 3-month testing/vaccination disposition statuses. Covid testing/vaccination status may also be provided by subject showing a copy of their covid testing result and/or vaccination information. This may be provided in person, shown during a video call, emailed or texted as a picture. Finally, study staff will reach out to all study participants (N=800) at 3 months following baseline to collect information on testing and vaccination uptake among study participants and barriers and facilitators for both network members and study participants. During

this assessment, information on situation appropriate testing will be collected to better understand the circumstances and context of testing. At the time of this writing, situation appropriate testing includes testing if symptomatic, if exposed to someone with COVID-19 infection and if entering a congregate living setting. Only participants reporting symptoms, exposure, and/or congregate housing will be included in the primary testing outcome analysis; post-hoc analysis will include all participants tested irrespective of the situation/context.

Secondary Outcome. Two secondary outcomes will be assessed at the level of the secondary subjects (network member connected to primary participant): the probability of receiving at least one 1) test and 2) vaccination dose within 3 months of baseline. Network member information, including identifying information will be collected during the baseline assessment through specialized network canvas software (described above). The secondary outcome will be determined based upon self-report from participants during the 30 and 90-day follow-up surveys. Note that this information is collected based asking the study subject whether the social network contact underwent these activities and not from contact with or medical record data collection of the social network member. Analyses for our secondary outcome will account for variability in network size across individuals.

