others (Aim 1b). Because we will likely have limited power to detect small to medium sized interaction effects in subgroup analyses, we will consider these analyses exploratory, with the goal of generating insights to guide future work. Partial pooling within a Bayesian estimation framework⁷¹ will be used to avoid bias and address the issue of multiple comparisons when testing interactions. We will also include an indicator for time trends to control for potential changes in testing recommendations, vaccine availability, infection rates, or other factors that could impact testing and vaccination outcomes over the study. The small number of sites precludes inclusion of a site-level random effect so site will be included as a fixed effect to account for between site differences in participant characteristics and local epidemic trends. The clustered version of the robust (i.e., sandwich) variance estimator will be used in all analyses to ensure correct inference even in the presence of other sources of within-cluster correlation in the data not captured in the model.⁷² For the participant outcomes, the probability of testing and vaccination (binary outcomes) will be modeled using logistic or log binomial regression based on model fit and consistency with model assumptions. The total number of tested/vaccinated network members will be modeled using negative binomial regression with total network size as an offset to account for differences among participants in the number of named network members.⁷³ A second analysis will treat each network member as an observation (tested/vaccinated or not) and will model the likelihood that network members are tested/vaccinated using logistic regression with random effects at the level of the study participant. We will also include a fixed effect for site. This approach will also allow us to examine whether characteristics of the network members (e.g., trust, social influence and social control within a dyad) are associated with probability of testing/vaccination.

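### The network outcome is participant report only, and awareness of contacts' status may differ by arm; the plan neither measures this, sets a rule for unknown status, nor tests sensitivity to it.

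*Combined protocol and SAP*

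**What the plan says.** **Source of the outcome.** Under Secondary Outcome: "The secondary outcome will be determined based upon self-report from participants during the 30 and 90-day follow-up surveys". The same paragraph adds that the information comes from asking the participant and "not from contact with or medical record data collection of the social network member". The participants' own outcomes have an outside source (Primary Outcomes): "Outcomes will be ascertained specifically by testing/vaccine registry data held by city and state held vaccine registries", supported by documents that participants show and a 3-month interview.

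**What the arms are taught.** In Table 2, the second Motivational strategy includes "Knowing the network member's COVID-19 history (ie. prior infection, recent exposure". The fourth covers "what sort of follow-up is required to motivate network members who have yet to be tested/vaccinated after earlier conversations". The Education condition, as described, consists of messaging, self-affirmation and testimonial videos. It contains no training in following up contacts.

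**The 30-day call.** Under Mini-Booster Communication Session, both arms are asked about network members. Conversation strategies, troubleshooting and outreach goals are marked for the C3 (Motivational) arm only. On the caller: "The same staff member who provided the initial intervention will conduct the booster with a given participant in order to continue rapport building".

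**Analysis.** Under Primary and Secondary Outcome Analysis, the number of members tested or vaccinated is modelled by "negative binomial regression with total network size as an offset". A second model takes each member as a binary observation. Attrition and missing data offers multiple imputation or a fully Bayesian model for any missing data. It does not say whether a participant's not knowing a member's status counts as missing.

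**The concern.** A proxy report is positive only if the event happened and the participant knows of it, leaving false reports aside. The intervention is meant to change the first. Following up members who are not yet tested or vaccinated involves finding out who they are, so it may also change the second. Randomisation balances awareness at baseline. It does not balance awareness that one arm's training creates afterwards.

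The way the data are collected adds to this. At 30 days the person recording the report knows the arm, delivered its session and, for Motivational participants, sets outreach goals in the same call.

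What is at stake is the second half of Aim 1a, diffusion to network members, which is the study's central premise. With no change in members' behaviour, the planned comparison could still show a difference. Nothing in the planned data would let a reader tell the two explanations apart.

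**Working it through.** **1. Inputs from Power Calculations.** Overdispersion k = 2; two-sided alpha 0.05. Network testing: N = 800, mean members tested per participant 0.12 (control) and 0.25 (intervention). Network vaccination: N = 560, means 0.51 and 0.92. That section uses 2:1 allocation, while Study Design and Randomization say 1:1; both are shown.

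**2. Reproducing the plan's figures.** Under the negative binomial, P(any) = 1 − (1 + 2m)^(−1/2). For m = 0.12, 0.25, 0.51 and 0.92 this gives 10.2%, 18.4%, 29.6% and 40.7%; the plan states 10%, 18%, 30% and 41%. For power, use a Wald test of the log rate ratio:

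SE = √[(1/m0 + k)/n0 + (1/m1 + k)/n1]; power = Φ(ln(m1/m0)/SE − 1.96).

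- Testing, 1:1: ln(0.25/0.12) = 0.734, SE = 0.202, power 95% (91% at 2:1).
- Vaccination, 1:1: ln(0.92/0.51) = 0.590, SE = 0.159, power 96% (93% at 2:1).

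Both agree with the plan's statement of at least, or more than, 80%. Simulated negative binomial regression gave 94% to 96%.

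**3. No true effect, different awareness.** Assumptions, none of them in the documents:

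- true uptake is the same in both arms;
- an event is reported only if the participant knows of it, with no false reports;
- an unknown counts as a non-event;
- network size is similar by arm;
- the reported control mean equals the plan's control mean.

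The reported mean ratio then equals the awareness ratio r (Motivational over Education), and k is unchanged. Example for vaccination, 1:1, r = 1.25: ln r = 0.223; SE = √[(1/0.51 + 2)/280 + (1/0.6375 + 2)/280] = 0.164; z = 1.36; Φ(1.36 − 1.96) ≈ 0.27.

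Two-sided rejection (nominal 5%):

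| Assumed r | Vaccination 1:1 | Vaccination 2:1 | Testing 1:1 | Testing 2:1 |
|---|---|---|---|---|
| 1.11 (e.g. 90% v 100%) | 10% | 9% | 8% | 7% |
| 1.25 (e.g. 60% v 75%) | 27% | 25% | 18% | 16% |
| 1.5 (e.g. 50% v 75%) | 71% | 65% | 48% | 42% |

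At r = 1.5 and 1:1, simulation gave 70% and 49% in favour of the Motivational arm. An awareness ratio of 0.92/0.51 = 1.80 (vaccination) or 0.25/0.12 = 2.08 (testing) would by itself reproduce the whole design effect.

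**4. If unknowns are dropped instead.** Assume 20% true uptake in both arms. Education participants know 60% of events and 30% of non-events; Motivational participants know 75% and 60%. Reported uptake among known members is then:

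- Education: 0.12/(0.12 + 0.24) = 33%;
- Motivational: 0.15/(0.15 + 0.48) = 24%.

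The ratio is 0.71, against the Motivational arm, with no true effect. The direction therefore depends on how unknowns are handled.

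**The case against.** A reader might infer that the plan codes unknown status as *no*, and hence that the bias always favours the Motivational arm. The documents do not support that. The offset and the binary member model describe the form of the model, not the coding of *don't know*, and the missing-data paragraph could send such answers to imputation. That objection stands, so direction and size are conditional. It does not remove the gap: the rule is absent, and a participant who simply answers *no* when unaware produces the same bias under any coding.

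A reader might also take the Table 2 item on history as training to learn testing and vaccination status. Its stated examples are prior infection and recent exposure. The link to status rests on the fourth strategy's follow-up of members not yet tested or vaccinated.

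Several features limit the problem. Networks are elicited before randomisation. Both arms are asked about contacts on the same occasions, and the network question is listed ahead of the coaching components of the booster. The documents do not say that the interventionist makes the 90-day call. With about 2 to 4 named members, often friends or family, awareness may be high in both arms; if it is 90% in Education, the ratio cannot exceed 1/0.90 = 1.11. All of this stands, and it makes a small bias possible. The plan collects nothing that would show whether the bias is small.

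Finally, the proxy source is openly stated, and keeping the same caller is a deliberate choice for rapport. Disclosing the source does not address differential awareness.

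**Conclusion.** The concern holds in conditional form. The documents establish a proxy-only outcome, follow-up training and coaching in one arm only, and a 30-day report taken by that arm's deliverer. They contain no measure of awareness by arm, no rule for unknown status and no sensitivity analysis for differential reporting.

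If unknowns are in effect counted as non-events, the bias favours the Motivational arm. Rejection under no true effect then runs from about 8–10% at an awareness ratio of 1.11 to 48–71% at 1.5 (1:1), slightly less at 2:1. The awareness ratios and the coding are assumptions. If unknowns are treated as missing, the direction is uncertain.

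A reader might extend this to the trial's primary result. The documents do not support that: the participant outcomes are registry-based and this mechanism does not reach them. The matter should be settled before follow-up, because awareness that was not recorded cannot be recovered later.

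**What to change.** 1. Record each named member's status at 30 and 90 days as yes, no or *don't know*, and report the share with known status by arm. Keep all named members in the denominator. Pre-specify bounds for the unknowns: all no, all yes, and scenarios that differ by arm. Use a known-status-only analysis as sensitivity only, since it conditions on a post-randomisation variable (step 4 of the working).
2. Have the network items self-completed before any booster coaching starts, or asked by existing site staff who did not deliver that participant's session. Staff Training and Fidelity already provides separate staff for each arm.
3. Describe the result as participant-reported network uptake, and claim diffusion only if it survives the bounds.

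**Cost.** Wider uncertainty on the network result, a little more survey coding, and slightly less rapport on those items. No extra participants, registry access or contact with network members is needed.

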- (4) previous direct or indirect exposure to law enforcement
- (5) has covid vaccination and applicable boosters (self-report, not required to show proof)

Exclusion Criteria:

- (1) inability to provide informed consent; and
- (2) active COVID-19 symptoms per CDC.⁵⁶

(3) Parolees currently living in a court ordered treatment center as part of parole and/or individuals otherwise meeting the definition of a prisoner

We include participants with prior COVID-19 vaccination (completed series) or recent COVID-19 infection in past 3 months given that they may be important change agents. We will remove the estimated numbers (n=160) who are vaccinated/recent infection from our primary analysis if there are no future vaccine boosters or new vaccines required (i.e., new variant). Candidate participants with COVID-19 symptoms will be referred for free testing at existing partners for each of the study sites.

Sex as a Biologic Variable. Both sexes and all genders will be included in this study with exploratory analyses to determine any differences in intervention effects.

STUDY VISIT PROCEDURES

[figure not shown]
Study procedures include:

- 1) Informed consent, locator form
- 2) Baseline survey with network elicitation
- 3) Randomization
- 4) Motivational or Education intervention (approximately 3 hours)
- 5) Booster/Communication 30-day \pm 7 days phone follow-up
- 6) 3-month follow-up phone survey \pm 7 days to assess participant and network COVID-19 testing/vaccination history

Eligible candidate study participants will undergo written informed consent. Following consent, study participants will complete a survey (Baseline Assessment) includes variables of interest and the social network inventory. Randomization will occur following the survey, and participants will be assigned to one of two concurrent Motivational or Educational group-level sessions. Sessions will be held weekly, also with availability, in the evening or on weekends. Study staff will be notified of group allocation and bring study participants to the appropriate group session/intervention rooms.

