Primary and Secondary Outcome Analysis. Two sets of analyses will be performed. The first will focus on testing and vaccination among participants and the second will focus on testing and vaccination among the networks of participants. Testing and vaccination will be analyzed as separate outcomes throughout. The primary outcome analysis will compare the probability of testing and the probability of vaccination among participants assigned to Educational vs. Motivational intervention. Secondary analyses will compare the total number of network members tested and vaccinated and the probability of testing/ vaccination among network members of participants assigned to Educational vs. Motivational intervention (Aim 1). All analyses will use generalized linear models with link functions based on the distribution of the outcome (logistic or log binomial for binary outcomes; negative binomial regression for count outcomes) and random effects as appropriate to account for clustering of network members within participants. The initial analysis will include an indicator for intervention assignment as the only independent variable and will not adjust for covariates since the randomization should ensure comparability between the groups on measured and unmeasured confounders, though group characteristics at baseline will be inspected visually for imbalances (Aim 1a). We will then incorporate participant (e.g., mental health, early adopter status) and network level (e.g., network thresholds, density) covariates to improve the precision of the estimates and to identify sociodemographic and network characteristics associated with differences in testing and vaccination yield. In addition, we will explore interactions between intervention group (Education vs. Motivational intervention) and participant characteristics to determine whether the intervention is more effective in certain groups than

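### Randomisation is stratified by site and prior infection/vaccination, but the initial vaccination analysis contains arm alone; naming the stratification factors in the primary model would be a minor, near-free gain in power

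*Combined protocol and SAP*

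**What the plan says.** All places are in the combined protocol and SAP.

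- **Randomization paragraph (Study Visit Procedures).** Allocation is 1:1 at participant level: "Randomization will be stratified by site as well as by key participant characteristics such as prior infection/vaccination, to ensure balance". No blocking method is named, and prior infection/vaccination is an example that is not defined further.
- **Primary and Secondary Outcome Analysis, Aim 1a.** "The initial analysis will include an indicator for intervention assignment as the only independent variable and will not adjust for covariates". The reason given is that randomisation should make the arms comparable. Participant and network covariates come later, to improve precision; the examples listed do not include a stratification factor.
- **Same section, after the Aim 1b text.** "site will be included as a fixed effect to account for between site differences", with no model named. For the participant outcomes the section then gives the link: "For the participant outcomes, the probability of testing and vaccination (binary outcomes) will be modeled using logistic or log binomial regression based on model fit". After the network-member model it adds "We will also include a fixed effect for site".
- **Same section, variance.** "The clustered version of the robust (i.e., sandwich) variance estimator will be used in all analyses". The cluster unit is not stated.
- **Inclusion and Exclusion Criteria.** Inclusion criterion 5 asks for self-reported vaccination and applicable boosters. The same section says "We include participants with prior COVID-19 vaccination (completed series) or recent COVID-19 infection in past 3 months" and then "We will remove the estimated numbers (n=160) who are vaccinated/recent infection from our primary analysis if there are no future vaccine boosters".
- **Power Calculations.** The vaccination sample is 560, after setting aside 30% as fully vaccinated or infected within 6 months.
- **Attrition and missing data.** Everyone enrolled is to be analysed.

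**The concern.** A design that stratifies on factors thought to matter usually carries them into the primary model. The plan's reason for leaving covariates out, comparability of the arms, addresses confounding and not precision. The plan itself expects sites to differ in participants and local epidemic trends, so site may well predict vaccination.

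If it does, two things follow for an arm-only test. It loses some power. And if allocation is balanced within strata, its standard error is a little too large, so it rejects slightly less often than 5% under the null. The plan also leaves open which participant model is primary: a general site fixed effect cannot belong to a model whose only term is arm.

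**Working it through.** **Inputs.** From Power Calculations: N=560, 30% versus 42%, two-sided 5%, 80% power, computed at 2:1. From the Randomization paragraph: 1:1. From Table 1: sites of 150, 250, 250 and 150, which at N=560 scale by 560/800 to 105, 175, 175 and 105. Site-specific vaccination rates are not given, so their spread is assumed.

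**1. The plan's own figure.** Power = Φ[(d − 1.96·SE0)/SE1], with SE0 pooled and SE1 unpooled.

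- 2:1 (186.7 and 373.3): pooled rate 0.38, SE0 = √(0.38×0.62×(1/186.7+1/373.3)) = 0.0435, SE1 = √(0.21/186.7+0.2436/373.3) = 0.0422. Power = Φ(0.82) = 79.5%, which reproduces the stated 80%.
- 1:1 (280 each): pooled rate 0.36, SE0 = 0.0406, SE1 = 0.0402. Power = Φ(1.01) = 84.3%. This is the base for what follows.

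**2. Arm-only versus site-adjusted risk difference.** 200,000 simulated trials per scenario, participants independent, site rates equally spaced on the logit scale and calibrated to 30% and 42% overall. Power in %:

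| Control rates across sites | Exactly 1:1 within site: arm-only / adjusted | Not balanced within site: arm-only / adjusted |
|---|---|---|
| equal | 84.5 / 84.4 | 84.6 / 84.3 |
| 25–35% | 84.6 / 84.6 | 84.6 / 84.5 |
| 20–41% | 84.8 / 85.3 | 84.5 / 85.1 |
| 16–46% | 85.2 / 86.3 | 84.3 / 86.0 |
| 13–52% | 85.6 / 87.5 | 84.5 / 87.4 |

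The largest gain is 87.5 − 85.6 = 1.9 points with balance and 2.9 without. With equal site rates the cost is 0.1 and 0.3.

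**3. Type I error.** With exact balance, arm-only rejection under the null falls from 5.1% (equal rates) to 4.1% (13–52%); site-adjusted stays at 5.0–5.1%. Without balance, arm-only is 5.0–5.2%.

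**4. A second layout.** Blocks of 4 (assumed), logistic Wald tests, 6,000 trials per scenario, two sites low and two high. Arm-only versus arm plus site: 84.5/84.6% (equal), 83.9/84.3% (25/35%), 85.5/86.6% (20/40%), 85.5/88.3% (15/45%). The last is the most polarised layout, which is why its gain, 2.8, exceeds 2 points even with blocking. Hand check of its null size: the between-site share of variance is 0.15²/(0.30×0.70) = 0.0225/0.21 = 0.107, so size is about 2[1 − Φ(1.96/√0.893)] = 2[1 − Φ(2.07)] = 3.8%. The simulation gave 3.7%.

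**5. Prior infection/vaccination.** The possible analysis sets are 800 (all enrolled), 800 − 160 = 640, and 800 × 0.70 = 560. Whether the factor varies in them depends on how it is defined at randomisation and on criterion 5, which read literally leaves vaccination status almost constant. As illustration only: if it did vary at N=560 (assumed share 14–43%, assumed logit shift 0.5 to 1 either way, site range 1 logit), adding it to a model with site gave a further 0.1 to 1.3 points. The documents support none of these inputs.

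**The case against.** The best reply is that site may already be covered. The general site sentence speaks of participant differences, the next sentence refers to all analyses, and the later site sentence for the network-member model would be redundant if the general one covered only network models. That stands as a possible reading. A reader might infer that the plan definitely omits site from the participant analysis; the documents do not settle it. They do leave two statements that cannot both describe one primary model.

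A reader might also infer that prior status varies in every analysis set. That does not follow: the factor is undefined, it could coincide with the group removed, and criterion 5 points towards near-constant vaccination status.

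The gain is small and rests on assumed site rates. At 25–35% it is essentially nil, and arm-only power stays at or above about 84% throughout, above the planned 80%. A steeper case (14/22/36/58% with the fixed odds ratio of 1.69) gives 77.6% arm-only against 80.8% adjusted, which might suggest that adjustment rescues the trial. It is not like for like: control averages 31.6% and intervention 42.5%, a difference of 10.9 points and not 12, so much of the shortfall is a smaller effect. The 2:1 versus 1:1 discrepancy moves power by about 5 points (79.5% to 84.3%), more than this change does.

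Nor is adjustment wholly free. It costs 0.1 to 0.3 points if site is irrelevant. In the illustrations with prior status, null rejection of the full model ran from 4.9% to 5.4%; the top value, 5.37%, is about 3.4 simulation standard errors above 5% (√(0.05×0.95/40,000) = 0.11 points). That is a slight excess, but not strictly none.

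**Conclusion.** This is a minor efficiency and clarity point on the vaccination outcome. The arm-only test gives up about 0 to 2 points of power when allocation is balanced within site and up to about 3 when it is not, or when site rates are sharply polarised. Adjustment costs about 0.1 to 0.3 points if the strata are irrelevant. The contribution of prior status is conditional and cannot be sized from the documents.

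A reader might infer that ignoring the strata makes the primary test invalid. It does not: as far as stratification goes, the arm-only test is at its nominal level or slightly conservative, and conservative only if allocation is balanced within strata and the strata predict outcome.

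The conclusion assumes N=560, 1:1, 30% versus 42%, assumed site rates, independent participants and participant-level robust variance. Correlation within the group sessions of 8 to 10, and the unnamed cluster unit of the sandwich variance, are separate questions not settled here. The testing outcome, with about 80 eligible participants, is left alone.

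**What to change.** In Primary and Secondary Outcome Analysis, replace the arm-only statement for vaccination and tie the site term to a named model, for example:

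*The primary vaccination analysis is a logistic regression on intervention arm, site (fixed effect, four levels) and prior infection/vaccination as recorded at randomisation where it still varies in the analysis set. The result is reported as a standardised risk difference or risk ratio with 95% CI and participant-level robust variance. The arm-only model is a sensitivity analysis.*

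The Randomization paragraph should list and define the stratification factors, so that the terms are known before the data are seen.

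Cost: wording only, since these factors are recorded before randomisation. Expected events at N=560 are 280 × 0.30 = 84 and 280 × 0.42 ≈ 118, about 202 in all, ample for five parameters (intercept, arm, three for site) or six with prior status. Standardisation keeps the result on a marginal scale, avoiding a conditional odds ratio, and the primary vaccination model gives up the log-binomial option.
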